9.4.1.3 Eligibility Confirmation and Enrollment

Once eligibility is confirmed, and all consents are fully executed, the candidate will be considered enrolled in the study. The enrollment procedures will be captured through a centralized process managed by the CTN Data and Statistics Center (DSC). Patients who do not complete screening or who are otherwise found to be ineligible for participation in the Full Study will be considered screen failures. These individuals who fail screening or refuse Full Study participation, may be assessed for Limited Study participation (section 10.15).

9.4.1.4 Baseline Procedures

Baseline procedures will continue with structured assessments on quality of life, substance use, and healthcare utilization. See Table 3 for a complete list of study assessments. Baseline procedures will ideally be completed at or within 72 hours of ED discharge by research staff via medical records abstraction and interview with study participants.

9.4.1.5 Intervention

All patients who screen positive for non-medical opioid use will receive an informational pamphlet related to OUD treatment and harm reduction.

9.4.1.6 Follow-up Visit (Day 30)

The follow-up research visit will assess engagement in treatment on the 30th day after discharge from the index ED visit. At the follow-up visit, participants will be asked to provide a urine sample and complete specified research assessments (see Table 3: Schedule of Assessments).

9.4.1.7 Participant Retention

Rigorous retention strategies will be employed to maintain contact with participants throughout the duration of the study and to minimize missing data. Broadly, retention methods may include outreach to the participant and their identified contacts through mailed letters, email reminders, phone calls, text messaging, social media, in-person contact, and/or public database searches. All tracking and retention materials will be IRB-approved.

9.4.1.8 Premature Participant Withdrawal

All participants will be followed for the duration of the study unless they withdraw consent, die, or the investigator or sponsor decides to discontinue their enrollment for any reason. Reasons for the investigator or sponsor terminating a participant from the study may include, but are not limited to, clinical documentation post enrollment that the patient is not a candidate for ED-initiated BUP, the participant becoming a threat to self or others, lack of funding, or DSMB early termination of the study for safety or effectiveness reasons.

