4.3 Secondary Effectiveness Aims

1. To evaluate patient-level outcomes 30 days after ED discharge and changes from pre-IF among CTN-0079-A1 study participants who received ED-initiated/expedited BUP, including non-medical opioid and other drug use (self-report using TLFB; urine toxicology), healthcare utilization, quality of life, and other patient-reported outcomes (PROMIS-29, PHQ-9, Treatment Effectiveness Assessment (TEA), treatment satisfaction, risk

behaviors, overdose events, and other drug-related consequences).

- a. Secondary analyses will evaluate the participant subgroups who received ED-initiated BUP and ED-expedited BUP separately as well as those who did not receive BUP.

All the above secondary effectiveness analyses will be performed for Full Study participants. Additional secondary analyses for limited study participants will be performed for available effectiveness outcome measures, as listed in the table of assessments.

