7.2 Full Study Population Eligibility Criteria

7.2.1 Inclusion Criteria

1. 18 years of age or older
2. Be able to speak English sufficiently to understand study procedures
3. Be a potential candidate for ED-initiated BUP by meeting either of the following two criteria:

- a. Clinical determination: Clinical documentation indicating the patient is a willing and eligible candidate for ED-initiated BUP or for whom this can be reasonably inferred, including any patient who receives ED-initiated BUP (via direct administration, prescription, or direct referral/transfer to BUP provider within 24 hours of ED discharge).
- b. Research determination: Both a and b below must be true at the time of study enrollment:
 - a) Assessment conducted by an RA indicates that the patient- (all must be true):
 - i. has had nonmedical opioid use within the last 7 days,
 - ii. meets DSM-5 criteria for moderate or severe OUD,
 - iii. denies methadone use within 72 hours of ED visit registration,
 - iv. is not engaged in formal MOUD treatment,
 - v. is not prescribed opioids for chronic pain management,
 - vi. reports being interested or “not sure” if interested in receiving BUP as elicited on the ED Health Survey during the index ED visit.
 - b) Absence of clinical documentation associated with the ED visit indicating that the patient is not a candidate for ED-initiated BUP.

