- Operationally, ED-expedited BUP is a warm hand-off to a provider who can provide (dispense and/or/prescribe) BUP within 24 hours of discharge from the ED. To be included, there must be confirmation of this handoff, inclusive of clinical documentation in the EMR of medical decision making indicating that the patient is being handed off/referred for BUP treatment to a specific provider, clinic, or service with the capacity and availability to provide BUP within 24 hours of the patients' ED discharge. This could include a patient being given an appointment at a specific time and location, transfer to a provider, facility, or inpatient service directly from the ED, or through a pre-arranged follow-up mechanism in which a treating provider/facility has agreed to accept patients referred from the ED. Such agreements often exist to ensure access to urgent follow up care after ED discharge (for other medical problems and, more recently, OUD) as it may not be practical or possible to schedule appointments, particularly outside of traditional business hours. Neither confirmation of a completed appointment (i.e., patient shows up and is seen) nor receipt of BUP at the dedicated follow-up appointment will be required as privacy regulations may preclude our obtaining these data and as the patient and treating provider may elect to treat with alternative regimes (e.g., methadone, naltrexone).
- Candidate for ED-initiated BUP (denominator): In the parent study, the denominator included patients with clinical documentation of non-medical opioid use and documentation: (a) affirming eligibility and willingness to receive ED-initiated BUP (or for whom this could be reasonably be inferred) or (b) confirming receipt of BUP administered or prescribed as part of the ED visit. For the ancillary study, we will include all patients identified to have non-medical opioid use and exclude only those for whom there is documentation or other evidence of the patient *not* being eligible or willing to receive ED-initiated BUP (or for whom this could be reasonably be inferred). Rationale: The rationale for this change is that it should provide more complete capture (expect higher sensitivity and lower specificity) and hold the sites more accountable for ensuring

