12.7 Tertiary and Exploratory Analysis

These will include (1) evaluating implementation and effectiveness outcomes over the course of the CTN-0079 parent and CTN-0079-A1 ancillary studies and conducting comparisons between each of the defined 6-month Implementation (i.e., parent study), Post-IF, and Maintenance Periods for which comparable data exists; (2) Testing several permutations of the primary implementation and effectiveness outcomes. For example, (i) permutations of how the numerator or denominator are defined and how these data are collected for the primary implementation outcomes (e.g., excluding referrals; including only patients identified through EMR documentation) (ii) permutations to effectiveness outcomes and analyses will include evaluation of linkage and engagement over different timeframes (e.g., linkage within 72 hours, 14 days, and 30 days; time-to-event analyses), evaluating alternative denominators (e.g., including participants who did not receive ED-initiated BUP), and alternate means of how these data are captured and defined (e.g., claims and other administrative data). Other analyses will include comparing the agreement of quality measures assessed using administrative data to the gold standard data collected through the clinical research assessments and identifying patient-level characteristics as well as structural and process measures associated with measure completion and effectiveness. See section 8.3 for more details on tertiary and exploratory outcomes.

Analyses of tertiary and exploratory outcomes may use the same approaches used for primary and secondary outcomes. Additionally, time-to-event analyses may be conducted for linkage and engagement time-to-event outcomes.

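### Section 9.4.1.8 lets follow-up end on later charting of non-candidacy; this can reach only participants who did not receive BUP and can bias analyses of that group in either direction

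*Combined protocol and SAP*

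**What the plan says.** Section 9.4.1.8, which sits under the Full Study procedures, follows participants "unless they withdraw consent, die, or the investigator or sponsor decides to discontinue their enrollment for any reason". Its examples of reasons for termination include "clinical documentation post enrollment that the patient is not a candidate for ED-initiated BUP". The list is permissive: it says what the reasons may include.

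Section 7.2.1 gives two routes to candidacy. The clinical route (3a) covers patients documented or reasonably inferred to be willing and eligible, "including any patient who receives ED-initiated BUP (via direct administration, prescription, or direct referral/transfer to BUP provider within 24 hours of ED discharge". The research route (3b) rests on the research assistant's assessment plus "Absence of clinical documentation associated with the ED visit indicating that the patient is not a candidate for ED-initiated BUP". Its timing is explicit: "Both a and b below must be true at the time of study enrollment".

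Section 8.1.1, writing about the implementation denominator, treats non-candidacy as "documentation or other evidence of the patient *not* being eligible or willing to receive ED-initiated BUP". It therefore covers unwillingness as well as ineligibility.

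Non-recipients are analyzed. Sections 4.3 and 12.3.3.2 plan secondary effectiveness analyses of the recipient subgroups "as well as those who did not receive BUP". Sections 8.3 and 12.7 plan exploratory denominators "including participants who did not receive ED-initiated BUP".

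**The concern.** Eligibility by the research route is settled at enrollment, but Section 9.4.1.8 allows it to be reopened on information that arrives later. That information is tied to treatment received. A note of non-candidacy goes with not being given BUP, while receipt of BUP makes a participant a candidate whatever else is charted. A post-enrollment event can thus end follow-up for part of one analysis group and for none of the other.

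Two things are at stake. The reported Day 30 engagement of non-recipients, and any contrast with recipients, may describe a selected remainder of those enrolled. The selection may also differ among the three sites, because it depends on how fully each one charts. Once a participant is discontinued, the Day 30 interview, urine screen and self-reported use are not collected, so no later analysis can undo the selection.

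**Working it through.** The plan states no figure on this point, so there is none to reproduce. The check sets the provisions side by side and then sizes the possible effect.

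**1. Whom the reason can reach.** Under Section 7.2.1 (3a), a participant who received BUP by administration, prescription or referral/transfer within 24 hours is a candidate. Later charting of non-candidacy can therefore apply only to someone who did not receive it.

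**2. Whether the sequence can occur.** The research route admits patients who are only unsure about BUP (7.2.1, 3b). Under Section 9.4.1.1, candidates not given BUP are not contacted after they leave the hospital, so they are recruited on site, when care and charting may be unfinished. Under Section 5.3, survey answers are not passed to clinical staff. A patient can enroll and then decline with the clinician. A chart completed later can also show a fact that was already true, such as current MOUD treatment.

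**3. Whether an analysis rule covers it.** Section 12.10 counts as failures those lost after receiving BUP. It has no rule for terminated participants or for non-recipients. Nothing else says whether terminated participants stay in any analysis.

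**4. Primary outcomes.** The primary effectiveness denominator is restricted to recipients (12.3.2), so this reason cannot alter it. The primary implementation outcome comes from the chart-review dataset (9.2.2) and does not depend on Full Study retention.

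**5. Size of the group.** Section 12.2 expects 300 × 0.40 = 120 Full Study participants and receipt of 40% to 90% among candidates. Applying that range to the 120 is an assumption. Non-recipients = 120 × (1 − receipt):

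- 40% receipt: 120 × 0.60 = 72
- 65% receipt: 120 × 0.35 = 42
- 90% receipt: 120 × 0.10 = 12

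The numbers are probably smaller, because Section 9.4.1.1 prefers recipients for enrollment.

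**6. Size of the shift.** Let f be the share of non-recipients removed, k the engagement proportion in those kept and t that in those removed.

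Shift = k − [(1 − f)k + f·t] = f(k − t)

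The documents give none of these. Assume f from 10% to 30%, k = 40%, and t from 20% to 60%. Only the difference k − t matters, not the level. Shift in percentage points:

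| f | t = 20% | t = 40% | t = 60% |
|---|---|---|---|
| 10% | +2 | 0 | −2 |
| 20% | +4 | 0 | −4 |
| 30% | +6 | 0 | −6 |

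For the top corner, all enrolled = 0.70 × 0.40 + 0.30 × 0.20 = 0.34, and 0.40 − 0.34 = +0.06.

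**7. Against sampling error.** A simple 95% half-width at 40% is 1.96 × √(0.40 × 0.60 / n). This gives about 11 points at n = 72, 15 at n = 42 and 28 at n = 12.

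**The case against.** The strongest defense is that the clause corrects eligibility. The target population is candidates, Section 8.1.1 drops documented non-candidates from the implementation denominator, and Section 13.13 requires immediate notification when an ineligible participant is enrolled. This stands for charting of a fact already true at enrollment, such as existing MOUD treatment or opioids prescribed for chronic pain. Keeping such people may itself distort the non-recipient estimate. It does not stand for a later change of mind, because Section 7.2.1 tests candidacy at enrollment. The clause does not separate the two.

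Section 8.1.1 also leaves discrepancies between chart and research data to the MOP, which is not among the documents. That provision concerns identifying candidates; it does not settle whether an enrolled participant stays in follow-up.

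Three stronger readings are tempting:

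- A reader might infer that non-recipient engagement will be overstated, with decliners in mind. The documents do not support a direction. Someone later charted as already in treatment would plausibly be more likely to be engaged on Day 30, and removing that person lowers the estimate.
- A reader might infer that only non-recipients with no charted reason would remain. The ground is non-candidacy, not any reason for non-receipt. Section 2.1 describes patients whose withdrawal is not yet sufficient, or who may lack a waivered prescriber, and who remain candidates. Termination is also discretionary.
- A reader might carry the problem over to the primary outcomes. Steps 1 and 4 of the working rule that out.

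It is also fair that the assumed shifts are smaller than the sampling error of so small a group, and that Section 12.8 calls this a feasibility study. Both limit the importance of the point. Neither removes it, since the selection is avoidable.

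**Conclusion.** The point holds as a limited one. Section 9.4.1.8 permits selection after enrollment that can act only on participants who did not receive BUP, and no analysis rule covers those removed. It can bias the secondary and exploratory effectiveness analyses of that group. How often the discretion would be used is not stated.

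The shift is at most about 6 percentage points in either direction, and zero if those removed engage at the same rate as those kept. This rests on assumed inputs: 10% to 30% of non-recipients removed and a difference in engagement of no more than 20 points. A larger removed share or difference would give a larger shift.

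The case for a change is that it costs little and keeps the data needed for either target population, all enrolled or candidates only.

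**What to change.** 1. Delete this reason from Section 9.4.1.8. State that charting of non-candidacy made after enrollment is not a ground for discontinuing research follow-up, including under the general discretion in the same section. Deleting the example alone would leave that discretion able to produce the same removals.
2. State that participants assessed as meeting the criteria when enrolled stay in research follow-up: Day 30 visit, facility survey, safety tracking and data matching.
3. Add a flag for later documentation of non-candidacy. Record whether it reports a fact already true at enrollment or a later change, such as declining BUP.
4. In Sections 12.3.3.2 and 12.10, state that non-recipient analyses include all enrolled non-recipients, with a sensitivity analysis excluding those flagged as not meeting criteria at enrollment.

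The cost is some protocol text, one data field, and a small number of extra Day 30 visits and payments. The change concerns research follow-up only and alters no clinical rule.

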9.4.1.9 Participant Reimbursement

Participants will be compensated for their participation in the Full Study. Each will receive \$75 for completion of screening and baseline assessments and \$100 for the Day 30 follow-up visit.

9.4.2 Limited Study Participants

ED patients who do not meet Full Study eligibility criteria or who refuse Full Study participation may be eligible to participate in the Limited Study. Limited Study participants will be identified through the same recruitment process as Full Study participants; however, once candidates screen out for the Full Study (see sections 7.2 and 7.3), they will continue to be assessed for possible Limited Study participation. Limited Study participation will only be offered to those candidates who complete screening in person (i.e., patients who are no longer in the hospital will only be offered participation in the Full Study if they are eligible). Once all inclusion criteria and none of the exclusion criteria have been met, the candidate will be presented with an Information Sheet outlining the purpose of the Limited Study, information to be accessed, and how the information will be used. If the patient remains interested in participating, the patient will be asked to certify they have read and understand the study procedures, as well as, provide consent authorizing release of medical information and use of PHI and PII so that we may link their survey and other research data with administrative databases. The authorization period will be valid for two years from the date of signing (i.e., study enrollment) and one year retrospectively (candidates will have the ability to opt out of releasing retrospective data one year prior to study enrollment). The candidate will be provided sufficient time to read through both the medical release and information sheet and will receive a verbal explanation of study procedures suited to their comprehension level. Candidates will be given time to ask questions before signing the medical release and information sheet. Limited Study participants will receive a pamphlet on OUD and receive \$25 compensation for their time completing in person assessments. Limited Study participants will be enrolled into the project through a centralized process managed by the CTN Data and Statistics Center (DSC). Once the participant has completed screening and is enrolled into the Limited Study, all remaining assessments will be completed via chart review or available data and without participant input. See Table 3: Schedule of Research Assessments – Full and Limited Study. The data for these assessments will be abstracted via manual searches from

EMRs and databases (e.g., PDMP) according to procedures established in the parent study. We will also link Limited Study participants' PHI and/or PII to administrative data for the purposes of data matching, pending availability (Data Use Agreements) as will be done with the Full Study population and all adult ED patients screening positive for non-medical opioid use, via a Waiver of Consent.

10.0 RESEARCH ASSESSMENTS

10.1 Table 3: Schedule of Research Assessments – Full and Limited Study

Assessment*	All	Full Study		Limited Study
	Screening & Enrollment	Baseline	Day 30	Day 30
ELIGIBILITY				
Introductory Script/Permission for ED Health Survey	X			
ED Health Survey	X			
Verbal Consent	X			
DSM-5	X			
Additional Demographics	X			
Prisoner Status Assessment	X			
Patient Eligibility	X			
Enrollment (Inclusion/Exclusion)	X			
Written Informed Consent (i.e., compound authorization form) (Full Study only)	X			
Information Sheet (with authorization)(Limited Study only)	X			
Medical Releases	X			
GENERAL				
Demographics	X			
Locator Information Form		X	X	
Other Substance Use		X		
PROMIS-29		X	X	
Motivations, Attitudes and Expectations		X		
Study Completion			X	X
HEALTH SERVICES				
Inpatient Utilization		X	X	
Outpatient Utilization		X	X	
Health Status		X	X	
Healthcare Visit Logistics		X		
ED Visit Review		X		**
ED Visits and Hospitalizations			X	X
PROCESS OUTCOMES				
Engagement in Treatment - Patient			X	
Engagement in Treatment - Facility			X	X
Prescription Drug Monitoring			X	X
Treatment Satisfaction/Acceptability			X	
Treatment Effectiveness Assessment (TEA)		X	X	
OPIOID OUTCOMES				
Timeline Follow-Back (TLFB)		X	X	
Urine Drug Screen		X	X	
Overdose Events & Risk Factors		X	X	
SAFETY				
Safety Events		X	X	X
Mental Health Assessment ⁺		X	X	

* All participant-facing documents will be reviewed/approved by the IRB. Minor edits may be made to assessments (e.g., grammar, punctuation, directions, system programming, etc.) as needed. Assessments will only be submitted for re-review if information to be collected is changed (e.g., addition of new questions.).

**To be completed after enrollment and prior to Day 30 for Limited Study participants

[†]As triggered by participant responses on the HST form.

10.2 Eligibility

ED Health Survey: This assessment will be conducted with patient permission through a Waiver of Documentation of Informed Consent. It will include questions about illicit opioid use embedded in a general health and substance use screener that also includes questions about tobacco and alcohol use. This form will be completed via self-report and potentially supplemented via medical record abstraction (e.g., rather than re-asking data collected clinically, the RA may review data with the patient to ensure accuracy and minimize patient frustration associated with redundancy) for all study candidates.

The Diagnostic and Statistical Manual of Mental Disorders, Fifth Edition (DSM-5): The DSM-5 criteria are assessed during screening to determine a current diagnosis of moderate-to-severe opioid use disorder. This assessment will be completed electronically in eClinical and will be automatically scored.

Additional Demographics: The additional demographics form collects information on health insurance, income, employment patterns, and housing information. This form is completed once at screening for all study candidates.

Prisoner Status Assessment: The Prisoner Status Assessment is a brief form collecting information related to current detainment, house arrest and/or probation status to determine whether the candidate meets the definition of a prisoner as delineated in 45 CFR 46.303(c) at the time of the index ED visit. This form will be completed once at screening for both Full and Limited Study participants. Candidates meeting prisoner status at screening will not be enrolled in either the Full or Limited study.

Eligibility Measures: These forms collect information regarding study eligibility. The Patient Eligibility form documents eligibility criteria collected during screening. Prior to informed consent, the inclusion and exclusion criteria are assessed and documented on the Inclusion/Exclusion Checklist and Enrollment form. Only individuals who continue to meet study eligibility criteria are allowed to continue with the screening process, and enrollment. Both limited and Full Study participants will complete eligibility assessments.

